APPENDIX 8: QTC SUBSTUDY PROTOCOL

An Uncontrolled, Open-label, Substudy within APL-C-001-09 Clinical Study (ADMYRE) in Patients with Relapsed/Refractory Multiple Myeloma, Evaluating the Potential Effects of Plitidepsin on the QT Intervals of the Electrocardiogram.

1. INTRODUCTION

Plitidepsin showed no relevant cardiac toxicity during preclinical/toxicology studies. However, other cyclic depsipeptides have been linked to increased cardiac toxicity, and thus a retrospective study of the cardiac adverse events [e.g., rhythm abnormalities, myocardial injury events, electrocardiogram (ECG) alterations] that occurred in all patients treated with single-agent plitidepsin was conducted. This study showed that the frequency of these events was not different to that reported in the age-matched healthy population, thereby suggesting that plitidepsin has a safe cardiac risk profile in cancer patients.[1]

1.1. SUBSTUDY RATIONALE

An undesirable property of some drugs is their ability to delay cardiac repolarization, an effect that can be measured as prolongation of the QT interval on the surface electrocardiogram (ECG). The QT interval represents the duration of ventricular depolarization and subsequent repolarization, and is measured from the beginning of the QRS complex to the end of the T wave. A delay in cardiac repolarization creates an electrophysiological environment that favors the development of cardiac arrhythmias, most clearly torsades de pointes (TdP), but possibly other ventricular tachyarrhythmias as well. TdP is a polymorphic ventricular tachyarrhythmia that appears on the ECG as continuous twisting of the vector of the QRS complex around the isoelectric baseline. A feature of TdP is pronounced prolongation of the QT interval in the supraventricular beat preceding the arrhythmia. TdP can degenerate into ventricular fibrillation, leading to sudden death. While the degree of QT prolongation is recognized as an imperfect biomarker for proarrhythmic risk, in general there is a qualitative relationship between QT prolongation and the risk of TdP, especially for drugs that cause substantial prolongation of the OT interval. Because of its inverse relationship to heart rate, the measured QT interval is routinely corrected by means of various formulae to a less heart rate-dependent value known as the QTc interval. It is not clear, however, whether arrhythmia development is more closely related to an increase in the absolute QT interval or QTc. Most drugs that have caused TdP clearly increase both the absolute QT and the QTc (hereafter called QT/QTc). Documented cases of TdP (fatal and nonfatal) associated with the use of a drug have resulted in the withdrawal from the market of several drugs and relegation of other drugs to second-line status. Because prolongation of the QT/QTc interval is the ECG finding associated with the increased susceptibility to these arrhythmias, an adequate premarketing investigation of the safety of a new pharmaceutical agent should include rigorous characterization of its effects on the QT/QTc interval.[2]

1.2. SUBSTUDY DESIGN RATIONALE

Plitidepsin is an anticancer agent that should not be administered to healthy subjects. Plitidepsin is administered at maximum tolerated dose, so it cannot be tested safely at supratherapeutic concentrations, even in cancer patients.

The impact of the disease, together with age, comorbidities and comedications present in patients with cancer is such that they are unable to tolerate excessive testing. Therefore, the search for a precise characterization of the effects of the drug on the QTc must be carefully balanced against the feasibility of the study design. Furthermore, the duration of the QTc interval is a less-than-perfect marker of the risk of proarrhythmia.[3]

Patients with refractory malignancies and expected reduced survival could justifiably be excused from the burden of time-matched baseline ECG values and separate administration of a positive control.[4]

Therefore, this substudy will be conducted in patients who may benefit from the anticancer activity of plitidepsin at the recommended dose, such as those enrolled in clinical trial APL-C-001-09. The potential effects of a 5 mg/m^2 plitidepsin dose given as a 3-hour intravenous infusion on the QTc interval duration will be assessed when the patient is treated with plitidepsin for the first time (Day 1 of Cycle 1). In order to detect any delayed drug effect on the QTc interval, these investigations will be repeated at the second infusion of plitidepsin (Day 15 of Cycle 1), when the drug is expected to reach the steady state in spite of plitidepsin's long terminal half-life in blood, approximately 88 hours, although concentrations on Day 15 are negligible.

This substudy will be conducted at some of the sites participating in study APL-C-001-09.

Although the daily variability in QTc interval of cancer patients has not been well described, it may be even larger because enrolled patients are likely to have advanced age, concomitant medical problems and prior QT-prolonging chemotherapy.[5] For this reason, an intrapatient standard deviation of 18 milliseconds is assumed. To reduce intrapatient variability due to measurement error, it has been recommended that the baseline QTc be rigorously investigated and be expressed as the mean of multiple electrocardiogram assessments.[6] For this purpose, two sets of triplicate ECG tracings recorded before plitidepsin administration will be considered baseline assessments: one set before and one after prophylactic medication administration on Days 1 and Day 15.

Electrocardiogram assessments will be performed by means of continuous 12-lead ECG automated digital collection.

All digital ECG continuous recordings will be sent to a third-party central ECG laboratory for measurement of intervals, diagnostics of abnormalities and review of ECG waveform morphology review. This will prevent the potential introduction of bias during the analysis of ECG recordings.

1.3. DNA COLLECTION RATIONALE

Genetic variation can be an important contributory factor to interindividual differences in QT/QTc changes to drug exposure. The collection of an additional sample will allow for genetic evaluation of mutations associated with ion channelopathies in case marked drug-related changes of the QT/QTc interval are observed. Details are provided in Section 7.4 QT-Related Polymorphisms Assessment.

2. OBJECTIVES

Based on the aforementioned scientific background, the primary objective of the present substudy is to assess the potential effects of plitidepsin administered at a therapeutic dose on the duration of the QT/QTc interval, measured by ECGs, in patients with relapsed/refractory multiple myeloma.

Secondary objectives are: to evaluate QTc changes over the treatment period; to characterize the plitidepsin (real and estimated) whole blood concentration/QTc relationship (or PK/PD relationship); and to explore related ECG parameters.

3. OVERALL SUBSTUDY DESIGN

This is an uncontrolled, open-label, substudy within APL-C-001-09 clinical trial (ADMYRE) in patients with relapsed/refractory multiple myeloma, evaluating the potential effects of plitidepsin on the QT/QTc intervals of the ECG.

Patients will be enrolled as needed to ensure at least 36 evaluable patients with evaluable ECG data.

Patients will be admitted to the study site on Days 1 and 15 (at least 2 hours before plitidepsin administration) until completion of the pharmacokinetic (PK) blood sample collection scheduled at three hours after EOI. After completing all other baseline assessments on Days 1 and 15, a 12-lead continuous ECG recorder will be set in place and patients will be resting in a supine position for at least one hour prior to the start of the plitidepsin infusion (SOI).

Patients will be administered the prophylactic medication at 20-30 minutes before SOI.

Patients will be at the study site until completion of the PK blood sample collection at three hours after EOI and then will leave the study site. Patients will be asked to:

- keep calm and relaxed until the next day (i.e., at 21 hours after EOI), when the ECG recorder will be removed.
- remain in a supine position from 10 minutes before 6, 9 and 21 hours after EOI. Specific times will be reminded (see section 4.4 Patient's Card)

Meals on Day 1 and Day 15 should be standardized. Patients will have lunch at 1.5 hours after EOI, which must be completed at least 30 minutes before the next PK blood sample collection (i.e., 3 hours after EOI). The activities of patients at the study site will be modified to avoid strenuous effort or emotional excitement.

An additional blood sample (10 mL) may be collected on Day 1 prior to treatment to allow for genetic evaluation of mutations associated with ion channelopathies, in case marked drug-related changes of the QT/QTc interval are observed. Participation in the QT-related polymorphisms assessment is optional.

Details on the timing of the treatment and assessments are given in the substudy's Schedule of Assessments and Procedures (see below).

4. PATIENT DEFINITION

4.1. SUBSTUDY POPULATION

Patients will be enrolled in the substudy as needed to ensure that at least 36 patients have completed all required assessments (see Section 5.1).

The inclusion and exclusion criteria for enrolling patients in this substudy are described in the following sections.

4.2. PATIENT ELIGIBILITY

4.2.1. Inclusion Criteria

In order to be enrolled in the substudy, patients must satisfy the following criteria at screening for the main study:

- 1. Patient included in the clinical study APL-C-001-09 and randomized to the experimental arm (plitidepsin + dexamethasone).
- 2. Patient with voluntarily signed and dated informed consent to participate in the QT substudy.
- 3. A 12-lead ECG consistent with normal cardiac conduction and function, showing:
 - Sinus rhythm.
 - Pulse rate between 45 and 100 bpm.
 - QRS interval <120 ms.
 - PR interval <200 ms.
- 4. Blood pressure between 90 and 150 mmHg systolic, inclusive, and not higher than 90 mmHg diastolic.

- 5. Serum electrolyte levels within seven days prior to first infusion, \leq grade 1:
 - Ionic Ca^{++} : 1.0 1.5 mmol/L.
 - $K^+: 3 5.5 \text{ mmol/L}.$
 - $Mg^{++}: 0.5 1.23 \text{ mmol/L}.$

4.2.2. Exclusion Criteria

Patients who meet any of the following criteria will be excluded from participating in the substudy:

- 1. Has heart rhythm disturbances (e.g. atrial fibrillation), unusual T wave and U wave (if present) morphology, personal or family history of Long QT Syndrome, ECG findings of complete left bundle branch block, permanent ventricular pacemaker, or Brugada Syndrome.
- 2. Has any skin condition likely to interfere with ECG electrode placement, or a history of breast implant or thoracic surgery likely to cause abnormality in electrical conduction.
- 3. Prior exposure to anthracyclines at a cumulative dose of doxorubicin or equivalent greater than 450 mg/m².
- 4. Patients who at screening are on medication that is known to prolong the QT interval (refer to Appendix 7 of the main protocol). Patients must have been off these medications for a minimum of 48 hours prior to plitidepsin administration on Day 1 and Day 15.
- 5. History of illegal drug use or alcohol abuse within six months before study drug administration.

4.3. ACTIVITIES AND SUBSTANCES THAT PATIENTS MUST AVOID DURING THE SUBSTUDY

Potential patients must be willing to adhere to the following prohibitions and restrictions during the course of the substudy to be eligible for participation.

- 1. Must refrain from jogging, strenuous exercises of all types, and sunbathing from 48 hours before Days 1 and 15 until after the end of the continuous ~24-hour ECG recording on Days 1 and 15.
- 2. May not consume beverages containing alcohol from 24 hours before Days 1 and 15 until after the end of the continuous ~24-hour ECG recording on Days 1 and 15.
- 3. Must refrain from using any methylxanthine-containing products, (e.g., chocolate bars or beverages, coffee, tea, or colas) from 48 hours before Days 1 and 15 until after the end of the continuous ~24-hour ECG recording on Days 1 and 15.

4. Patients may consume standard meals during their stay at the study site. Meals will not contain spicy foods (i.e., black pepper, hot peppers, wasabi, etc). Excessive food consumption will not be permitted.

4.4. PATIENT'S CARD

The Investigator will provide the patient with a card listing all prohibited activities and substances during the substudy. This card will contain blank spaces for the Investigator to write down the specific times of the ECG timepoints at 6, 9 and 21 hours after EOI. The Investigator must remember to tell the patient that he/she must remain in a supine position from 10 minutes before these times.

5. PLAN OF SUBSTUDY

5.1. COMPLETION

A patient will be considered to have completed the substudy if he/she has evaluable ECG data.

5.2. WITHDRAWAL/DISCONTINUATION FROM THE SUBSTUDY

A patient will be withdrawn from the substudy for any of the following reasons:

- Withdrawal of substudy ICF.
- The patient does not comply with the substudy requirements, including inclusion criteria, exclusion criteria, and prohibitions and restrictions.

Patients who withdraw from the substudy will be replaced as needed in order to ensure that at least 36 evaluable patients complete the substudy.

5.3. WITHDRAWAL FROM QT-RELATED POLYMORPHISMS ASSESSMENT ONLY

A patient may withdraw his/her consent for the QT-related polymorphisms assessment while being evaluable for the substudy. In such a case, collected blood samples will be destroyed. To initiate the sample destruction process, the Investigator must notify the Sponsor's center contact and request sample destruction. In turn, the Sponsor's center contact will ask the central lab contact to destroy the sample. If requested, the Investigator will receive written confirmation from the Sponsor/central lab that the sample has been destroyed.

6. TREATMENT

6.1. PROPHYLACTIC MEDICATION

During the substudy (Cycle 1 of main study), all patients must receive the following prophylactic medication at 20-30 minutes before infusion of plitidepsin:

- Palonosetron 0.25 mg i.v. (tropisetron 5 mg i.v. could be considered if palonosetron is not available).
- Dexchlorpheniramine 5 mg i.v. or chlorpheniramine 10 mg i.v., (dexchlorpheniramine 6 mg p.o. or chlorpheniramine 10-15 mg p.o. could be considered, if i.v. formulations are not available).
- Ranitidine 50 mg i.v. or cimetidine 300 mg i.v.

Oral aprepitant may be used as per Investigator's criteria/institutional guidelines. Metoclopramide should be avoided.

The use of alternative prophylactic medications should be discussed in advance with the Sponsor.

6.2. PROHIBITED MEDICATIONS/THERAPIES

Drugs known to prolong QT interval and/or induce torsades de pointes are prohibited (refer to Appendix 7 of the main protocol). Patients must have been off these medications for a minimum of 48 hours prior to plitidepsin administration on Days 1 and 15.

7. SUBSTUDY EVALUATIONS

7.1. SUBSTUDY PROCEDURES

The substudy's Schedule of Assessments and Procedures summarizes the frequency and timing of continuous ECG recorder placement for pharmacodynamic (PD) assessments and PK and QT-related polymorphisms sample collection.

A 10 mL blood sample will be collected on Day 1 from patients who have consented to participate in the QT-related polymorphisms assessment of the substudy.

7.2. PHARMACOKINETIC EVALUATIONS

Plitidepsin PK assessment in patients participating in the substudy will be the same as the one conducted on patients in Arm A of the main study. Please refer to the main study protocol, Section 6.2.

7.3. PHARMACODYNAMIC EVALUATIONS

Patients will wear a continuous ECG recorder on Days 1 and 15, from prior to prophylaxis administration to 21 hours after EOI. This ECG recorder will be provided by ERT after the study site has registered online at ERT's MYSTUDY PORTALTM. Registration details will be provided to the site coordinator at each participating site.

The ECG recorder will be set in place once all safety assessments scheduled for the main study (i.e., vital signs, blood sample extraction for laboratory tests, and ECG) have been conducted.

On Day 1 and Day 15, serial ECGs with stable resting heart rate will be extracted from the continuous recording in triplicate (three 10-second digital ECGs in close succession) within a 10 minute (\pm 5min) window at each scheduled time point of the ECG assessments:

• Pre-prophylaxis (Predose 1), post-prophylaxis and prior to SOI (Predose 2)*, 1.5 after SOI, just before the end of infusion (EOI)*, 0.5, 1*, 3*, 6, 9, and 21 hours after EOI.

*Triplicate ECGs will be extracted prior to the corresponding PK blood sample collection.

Patients will remain in the same comfortable supine position for at least 10 minutes before and after the time points for ECG and PK collection. Physical activity, external stimulation, and meal ingestion should be regulated to keep activity and emotional excitement to a minimum. ECG recordings at time points 6, 9 and 21 hours after EOI will be ambulatory.

All digital continuous ECG recordings will be sent to a third-party, central ECG laboratory (for triplicate ECG extraction at the scheduled time window, measurement of intervals, diagnostics of abnormalities and review of ECG waveform morphology). Quality assurance procedures will be used to ensure high precision and consistency of QT interval measurements.

For the triplicate ECGs collected at each time point, the average of the three measurements for each ECG parameter will be considered for all listing and statistical analyses described below.

7.3.1. QT Correction Methods

QT will be corrected for heart rate using the following methods:

- Primary: Fridericia's correction method (QTcF).[7]
- Secondary: Bazett's correction method (QTcB).[8]

7.3.2. Pharmacodynamic Endpoints

In principle, for each patient and each postdose time point on Day 1 and Day 15, baseline QTc intervals will be the mean of the Predose 1 and Predose 2 QTc values for that patient on Day 1.

If the mean Predose 2 QTc value of all evaluable patients is ≥ 10 ms longer than of the mean Predose 1 QTc value, an effect of prophylactic medication on QTc cannot be ruled out; therefore, individual Predose 2 QTc values will be considered as the baseline values.

The change from baseline (ΔQTc) will be calculated using the corresponding baseline QTc values. Specifically:

• ΔQTc at time t: Difference in QTc between scheduled time point t and baseline.

The primary pharmacodynamic (PD) endpoint will be ΔQTc at each scheduled time point. ΔQTc will be summarized where QTc is derived using both the QTcF and QTcB correction methods whereby QTc denotes a general notation of corrected QT using either method.

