7.4.1. Confidentiality of Samples for QT-related Polymorphisms Assessment

PharmaMar shall comply with the Directive 95/46/EC of the European Parliament and of the Council of 24 October 1995 on the protection of individuals with regard to the processing of personal data and on the free movement of such data.

Appropriate technical and organizational measures to protect the genetic data against unauthorized disclosures or access, accidental or unlawful destruction, or accidental loss or alteration will be put in place. Sponsor personnel whose responsibilities require access to personal data agree to keep the identity of substudy patients confidential.

Samples will be stored until the ECG database has been locked, when the decision on whether it is necessary to rule out mutations associated with ion channelopathies, is made.

7.5. 12-LEAD ECG ACQUISITION

ECGs will be obtained digitally using a Mortara Instrument (Milwaukee, WI, USA) H-12+ ECG continuous 12 lead digital recorder, which will obtain ECGs on Day 1 and Day 15. The ECGs are stored continuously on a flash card and will not be available for review until the card is received by ERT and analyzed. ECGs to be used in the analysis will be selected by predetermined time points as detailed below and will be read centrally using a high-resolution manual on-screen caliper semiautomatic method with annotations. In this trial using pre-treatment ECGs as the baseline, the H-12+ recording will be started approximately 1 hour prior SOI through approximately 21 hours post EOI in order to obtain the baseline ECGs as detailed below.

ECGs for the treatment days will be obtained as triplicate (3) 12-lead ECGs at each time point which will be downloaded from the H-12+ flash card approximately one minute apart on Day 1 and Day 15. On Day 1 and Day 15, baseline ECGs will be extracted (in triplicate) pre-prophylaxis (Predose 1), post-prophylaxis and prior to SOI (Predose 2). On Day 1 and Day 15, triplicate ECGs will be extracted at the following time points: 1.5 after SOI, just before the EOI, 0.5, 1, 3, 6, 9 and 21 hours after EOI.

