8.2. PHARMACODYNAMIC ANALYSES

The primary objective of this substudy is to measure the potential effect of plitidepsin on QTc. The primary comparison of interest will be Δ QTc at each scheduled time point. A non-inferiority criterion of 20 ms will be used to establish that postdose QTc is not inferior to baseline. Evaluable patients who have evaluable ECG data will be included in the primary analysis.

A mixed effect analysis of variance (ANOVA) model will be fitted with the QTc data as the dependent variable and intervention (baseline *vs.* postdose), scheduled time point t of measurement (where t will be baseline, 1.5 after SOI, just before the EOI, 0.5, 1, 3, 6, 9 and 21 hours after EOI) and treatment period (Day 1 and Day 15) as fixed effects and patient as a random effect. Using the estimated least square means and intrapatient variance obtained from this model, a one-sided 95% CI will be calculated for the

difference in mean QTc between baseline and each scheduled time point t. Non-inferiority will be concluded if at each scheduled time point the upper-limit of the one-sided 95% CI falls below 20 ms.

Mean ECG parameters (QT, QTc, RR, heart rate, QRS, and PR) and corresponding changes from baseline will be listed and summarized descriptively by time point t. Plots of mean QTc changes from baseline (Δ QTc) *vs*. the scheduled time point t will be prepared.

The incidence count and percentage of patients with QTc increase from baseline $(\Delta QTc) > 30-60$ ms and >60 ms will be tabulated for each time point t, age and gender. The incidence count and percentage of patients with any postdose QTc values >450 ms and >480 ms, will be tabulated for each time point t, and gender. Patients with QTc values >500 ms will be listed.

The incidence count of patients with PR >200 ms, QRS >120 ms, heart rate >100 bpm and <50 bpm, and ST segment and T and U wave abnormalities will be reported. The incidence count of patients with abnormalities in the ST segment (e.g. flat, depressed, elevated) and T wave (i.e. present or absent) and U wave (e.g. flattened, inverted, biphasic and notched) will be reported.

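### The QT substudy's baseline rule corrects for a premedication effect only when QTc lengthens; a persisting shortening of d ms would understate the QTc change by d/2

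*Protocol*

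**What the plan says.** Appendix 8 describes an uncontrolled substudy (section 3), so each patient's own baseline is the only comparator. Section 1.2 provides two triplicate ECG sets before plitidepsin, "one set before and one after prophylactic medication administration on Days 1 and Day 15". Section 3 gives the timing: "Patients will be administered the prophylactic medication at 20-30 minutes before SOI".

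Section 7.3.2 defines the reference for every post-dose time point on both days: "baseline QTc intervals will be the mean of the Predose 1 and Predose 2 QTc values for that patient on Day 1". The single exception opens with "If the mean Predose 2 QTc value of all evaluable patients is ≥ 10 ms longer" than the Predose 1 mean; in that case "an effect of prophylactic medication on QTc cannot be ruled out; therefore, individual Predose 2 QTc values will be considered as the baseline values". Nothing is said about a Predose 2 mean that is shorter, by whatever amount.

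Post-dose ECGs are extracted at "1.5 after SOI, just before the EOI, 0.5, 1, 3, 6, 9 and 21 hours after EOI" (section 7.5). Section 8.2 states the test: "A non-inferiority criterion of 20 ms will be used to establish that postdose QTc is not inferior to baseline". The one-sided 95% upper limit must be under 20 ms at each scheduled time point. Appendix 8 plans no analysis with Predose 2 as an alternative baseline. SAP section 8.12 refers the QTc analyses to a separate document, which is not among the two reviewed.

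**The concern.** The stated ground for changing the baseline has no direction. A Predose 2 mean 10 ms shorter than Predose 1 would be just as much a sign that premedication affects QTc. The rule nevertheless acts only on lengthening. When it fires, the group baseline rises by at least half of 10 ms and the estimated QTc change falls by the same amount. The mirror-image correction, which would raise the estimate, does not exist.

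In a safety non-inferiority test the harmful error is to understate the change. With no control arm, nothing else in the comparison can cancel a premedication effect. One Day 1 baseline serves all time points on Day 1 and Day 15, so an error in it moves them together. The same change from baseline also feeds the counts of increases above 30 and 60 ms (section 8.2) and the concentration-QTc model (section 8.3).

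**Working it through.** **The plan's own figure.** Section 8.1 gives SD 18 ms, 36 patients, margin 20 ms, true difference 5 ms, one-sided 5% and probability 80%. With two groups of 18, SE = 18 × √(2/18) = 6.0 ms and Φ((20 − 5)/6.0 − 1.645) = 80.4%. The stated figure is therefore reproduced, but by a two-group formula. The substudy is within-patient, so within-patient standard errors are used below. That discrepancy is not part of this point.

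**Standard errors.** Section 1.2 assumes an intrapatient SD of 18 ms. Read as a per-measurement SD with independent errors:
- Baseline averaged over two sets: 18 × √(1 + 1/2)/√36 = 3.67 ms.
- Predose 2 alone: 18 × √2/√36 = 4.24 ms.

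**Bias.** Let P be the QTc before premedication, d the shortening caused by premedication, and Δ the plitidepsin effect. Then Predose 1 = P, Predose 2 = P − d, and baseline = P − d/2.
- Premedication effect still present post-dose: (P − d + Δ) − (P − d/2) = Δ − d/2. The change is understated by d/2.
- Effect worn off: (P + Δ) − (P − d/2) = Δ + d/2. The change is overstated by d/2.
- Persisting lengthening of e below 10 ms, no switch: Δ + e/2. The change is overstated by less than 5 ms, which is conservative.
- Persisting lengthening of 10 ms or more, switch made: Δ, no bias. The trigger uses the observed group mean, so at a true lengthening of exactly 10 ms it fires only about half the time.

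**Single time point, true Δ = 20 ms, effect persisting.** Probability of passing = Φ((d/2)/3.67 − 1.645):

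| d (assumed) | Hidden (d/2) | P(pass) |
|---|---|---|
| 0 ms | 0 ms | 5% |
| 2 ms | 1 ms | 8% |
| 5 ms | 2.5 ms | 17% |
| 10 ms | 5 ms | 39% |
| 15 ms | 7.5 ms | 65% |

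With an SE anywhere from 4.24 down to 3.0 ms (the latter if 18 ms is the SD of the change), the ranges are 8–10% for d = 2, 15–21% for d = 5 and 32–51% for d = 10.

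**All time points together.** Suppose Δ is 20 ms at all eight post-dose points and d = 10. The eight results share a baseline error b with SD 18/√72 = 2.12 ms, and each post-dose mean has SE 18/√36 = 3.0 ms. The joint pass probability is the average over b of [Φ((5 − 1.645 × 3.67 + b)/3.0)]⁸ = 2.6%, or about 3%.

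**What a two-sided 10 ms trigger would do.** Simulated single-time-point pass rates at Δ = 20 ms (20,000 runs, variances estimated):

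| d | Rule as written | Two-sided trigger | Predose 2 always |
|---|---|---|---|
| 5 ms | 17% | 15% | 5% |
| 10 ms | 38% | 20% | 5% |
| 15 ms | 64% | 11% | 5% |
| 20 ms | 85% | 5% | 5% |

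At d = 10 the observed difference reaches the trigger only about half the time, so a two-sided trigger alone is a partial repair.

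**The case against.** The strongest answer is that nothing in the documents suggests that premedication shortens QTc. The direction they raise is prolongation. Appendix 7 lists ondansetron, granisetron and diphenhydramine, which belong to the main-study premedication (protocol section 7.5.1). The substudy uses a different regimen (Appendix 8, section 6.1) and bars QT-prolonging drugs (section 6.2). A trigger for lengthening follows the risk the plan had identified. This stands: d is hypothetical, and the case rests on the rule not matching its own reason.

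Four stronger readings are tempting, and the documents do not support them.
- A reader might infer that every change is understated by d/2. That would need the effect to persist undiminished to 21 hours after the end of infusion, about a day after premedication. Where it has worn off, the bias is conservative.
- A reader might take 39% as the chance of a wrong overall conclusion. It applies to one time point. It carries over to the conclusion only if a single point is near the limit and the others pass easily.
- A reader might blame supine rest rather than the drugs. Patients rest supine for at least an hour before infusion (section 3), and premedication comes 20–30 minutes before it, so Predose 1 should also be a resting ECG.
- A reader might call the rule anti-conservative throughout. A persisting lengthening below 10 ms errs the other way.

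Two further points limit the harm. Absolute QTc above 450, 480 and 500 ms is reported whatever the baseline (section 8.2). In the concentration-QTc model a constant shift enters the intercept and leaves the slope alone unless the intercept is dropped (section 8.3). Neither corrects the primary test. The separate QTc document may contain more, but this cannot be checked, and the rule in Appendix 8 would still read as it does.

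**Conclusion.** The concern holds in a limited form. The rule's reason covers both directions and its trigger covers one. A persisting premedication shortening of d would leave the QTc change understated by d/2 at the time points where it persists, with no upper bound under the rule. In effect the 20 ms limit becomes 20 + d/2 ms on the plitidepsin effect, for example 25 ms at d = 10.

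The pass rates of 8% to 65% for d of 2 to 15 ms, against 5%, rest on four assumptions: a d that the documents do not give, persistence to the time point in question, 18 ms as a per-measurement SD with independent errors, and one time point considered alone. The documents do not show that such a shortening occurs, or that the overall conclusion would probably be wrong. This is a minor defect of specification in a safety substudy, worth correcting because the correction is nearly free.

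**What to change.** In Appendix 8, section 7.3.2, and in the separate QTc analysis document:

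1. Make the trigger two-sided: use individual Predose 2 values as baseline when the group means of Predose 2 and Predose 1 differ by 10 ms or more in either direction.
2. Because this alone still leaves about 20% at d = 10 and 15% at d = 5, prespecify a sensitivity analysis that repeats the primary analysis with individual Predose 2 values as baseline regardless of the trigger. Using Predose 2 throughout is the alternative.

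The ECGs are already collected, so the cost is a few words and one extra table. With Predose 2 alone the SE is 4.24 instead of 3.67 ms. At a true 5 ms effect the probability of passing at one time point is then Φ(15/4.24 − 1.645) = 97%, against Φ(15/3.67 − 1.645) = 99%.

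A Predose 2 baseline is unbiased only while the premedication effect lasts. After a lengthening that has worn off by the late ECGs, it would understate the change there by the full lengthening. This favours reporting both baselines side by side over relying on either alone.
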